8.2 SAMPLE SIZE JUSTIFICATION

An a priori power analysis was conducted using G*Power version 3.1.9.7 (Faul et al., 2007) to determine the minimum sample size required to test the study aims. Results indicated the required sample size to achieve 86% power for detecting a medium effect, at a significance criterion of $\alpha = .05$, was $N = 42$ for within-between interactions on repeated measures.

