4.2 PARTICIPANTS

We will aim to recruit 42 adults who meet NIAAA criteria for at-risk drinking; >7/14 standard drinks per week for women/men, with at least one past-month heavy drinking episode defined as 4/5+ standard drinks for women/men. To ensure a range of alcohol use in the sample we will aim to recruit an even number of participants from AUDIT zones 1, 2 and 3 (AUDIT total score = 0-7, 8-15, and 16-19 respectively) which reflect different levels of alcohol use health risk severity [57]. The AUDIT is a validated screening tool that indexes alcohol use severity, but is not a diagnostic instrument. Typically an AUDIT score of 20 or greater indexes elevated risk for alcohol use disorder; those with scores of 20+ will be excluded. In addition, we will aim to recruit an even distribution of males and females across AUDIT zones. Participants will be recruited via flyers and social media ads from the triangle area (Chapel Hill, Raleigh, Durham). Interested participants will fill out an online pre-screen survey using Research Electronic Data Capture (REDCap) to determine initial eligibility. We estimate screening 250 people will yield 55 eligible participants to consent. Accounting for study drop-outs, we expect that 55 consents will allow for a final sample size of 42 who complete all study procedures, which is a feasible goal for the 12-month study. Potentially eligible participants will be contacted via email to schedule a virtual visit including additional screening and informed consent. A research assistant will explain the study requirements and both parties will sign the consent documents via REDCap if agreeing to enroll in the study. The DSM-5 SCID will then be administered to screen for alcohol and substance use disorder.

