To analyze study aim 3, multi-level regression models will be used to assess within-person changes on repeated measures along with between-person individual differences. A linear growth curve model will be used to test the hypothesis that alcohol-specific satiety increases with time and additional drinks. Timepoint (1-6) and drug (alcohol or placebo) will be included in the model as within subject factors. Compared to placebo, alcohol is predicted to be associated with higher rates of change (slope) in satiety. Next, AUDIT will be included as a continuous predictor of slope in the model to test the hypothesis that participants with fewer alcohol dependence symptoms (lower AUDIT scores) report reduced satiety. Finally, subjective craving scores (Alcohol Urge Questionnaire; AUQ) from each timepoint will be included in the model. The effect of satiety over time is expected to remain significant after controlling for craving. Alcohol-specific satiety is expected to be negatively associated with measures of reward and incentive motivation for alcohol (BAES, APT, Dot Probe). Outcomes from each of these measures will be included in separate multi-level models with satiety scores as the primary dependent measure and timepoint (1-6) and drug (alcohol, placebo) as within-subject factors to determine the effect of additional dependent measures on within-person change in alcohol specific-satiety over time (slope).

To analyze aim 4, a repeated measures analysis of variance (ANOVA) will be used to assess the effect of a dietary supplement on alcohol-specific satiety in a 2(alcohol, placebo) x 2(timepoints) design. It is

predicted that compared to placebo, a GLP-1 stimulating dietary supplement will increase alcohol-specific satiety.

To analyze aim 5, linear regression will be used to assess the association between HMGB1 levels as a function of BrAC during the laboratory alcohol sessions. Data processing and analyses will be completed in R and SPSS.

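### The 86% power at N = 42 is for a grouped within-between interaction that no aim-specific analysis contains; the closest planned test, continuous AUDIT on satiety slope, has about 50% to 69% power at conventional medium effects.

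*Combined protocol and SAP*

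**What the plan says.** Section 8.2 reports a G*Power calculation for the minimum sample size needed to test the aims: "Results indicated the required sample size to achieve 86% power for detecting a medium effect", at alpha 0.05, was 42, for "within-between interactions on repeated measures". It gives no numeric effect size, number of groups, number of measurements, correlation among measures or sphericity correction, and it names no aim. Section 4.2 (Participants) makes 42 the number of completers: "we expect that 55 consents will allow for a final sample size of 42 who complete all study procedures".

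Section 8.1 sets out the analyses:

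- **Aims 1 and 2:** multilevel models. The TAC-BrAC correlations are within-person.
- **Aim 3:** "Timepoint (1-6) and drug (alcohol or placebo) will be included in the model as within subject factors". Then "AUDIT will be included as a continuous predictor of slope in the model".
- **Aim 4:** repeated-measures ANOVA of "alcohol-specific satiety in a 2(alcohol, placebo) x 2(timepoints) design". Under Sections 4.1 and 4.3, each participant receives both supplement and placebo.
- **Aim 5:** linear regression of HMGB1 on BrAC.

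AUDIT zones and sex appear in Section 4.2 as recruitment targets. They are not factors in any aim-specific model.

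**The concern.** The procedure named in Section 8.2 tests whether change over repeated measures differs between groups of people. The factors named for Aims 3 and 4 vary within each participant, and AUDIT enters Aim 3 as a continuous score. The stated power therefore does not describe any aim-specific test as planned.

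The AUDIT hypothesis is where this matters most. It is the one person-level predictor that Section 8.1 ties to a directional aim-specific hypothesis, and it is closest in kind to the test that was powered. A reader who applies the 86% to it could take a null AUDIT result as good evidence against a medium association, when the power for that association may be far lower.

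**Working it through.** **Inputs.** From the documents: N = 42, alpha 0.05, a medium effect, and the within-between interaction family (Section 8.2); six timepoints, two drug levels and continuous AUDIT (Section 8.1); three AUDIT zones with the sexes balanced across them (Section 4.2). Assumed, because the documents give no values: f = 0.25 for medium in the ANOVA family, correlation among measures ρ = 0.5, sphericity ε = 1, and a two-sided test for AUDIT on slope.

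**1. The plan's own figure.** For k groups and m measures, λ = f²·N·m·ε/(1 − ρ), with df1 = (k − 1)(m − 1)ε and df2 = (N − k)(m − 1)ε. Power is the upper tail of the noncentral F beyond the 5% critical value. Example, k = 6 and m = 5: λ = 0.0625 × 42 × 5/0.5 = 26.25, df = (20, 144), power 85.9%.

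| Groups × measures | Power at N = 42 |
|---|---|
| 2 × 2 | 88.5% |
| 3 × 2 | 80.3% |
| 3 × 3 | 88.7% |
| 2 × 6 | 99.6% |
| 3 × 6 | 98.4% |
| 6 × 5 | 85.9% |
| 6 × 6 | 90.2% |

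At these settings, among layouts with 2, 3, 4 or 6 groups and 2 to 7 or 12 measures, only 6 × 5 rounds to 86%. Other inputs also reach it: 3 × 6 with ε = 0.5 gives 86.3%, and 3 × 3 with ε = 0.9 gives 85.9%. The figure is attainable, but the stated inputs do not determine it.

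**2. AUDIT as predictor of slope.** Treat this as a 1-df regression of each person's slope on AUDIT: λ = f²·N, df = (1, 40), with f² = r²/(1 − r²).

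- r = 0.30: f² = 0.09/0.91 = 0.0989 and λ = 4.15, giving 51%. The Fisher z approximation, with atanh(0.30) × √39 = 1.93 against 1.96, gives 49%.
- f² = 0.15: r = √(0.15/1.15) = 0.36 and λ = 6.3, giving 69%.
- One-sided, the same two effects give 61% to 64% and 79%.
- 86% at N = 42 needs r of about 0.43 (regression F) to 0.45 (Fisher z).
- If the slope is measured with reliability 0.7, a true r of 0.30 becomes 0.30 × √0.7 = 0.25, and power falls to 37%.

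**3. How the choice of medium drives the gap.** In the 2 × 2 case, f = 0.25 with ρ = 0.5 gives λ = 0.0625 × 42 × 2/0.5 = 10.5. Per person that is 10.5/42 = 0.25, so f² = 0.25 on the change score, or r = √(0.25/1.25) = 0.45. Power is 88.5%. The same word therefore covers effects with roughly 50% and 89% power.

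**4. Two-level within-person contrasts.** Paired t test with 41 df: dz = 0.50 gives noncentrality 0.50 × √42 = 3.24 and power 88.6%. At dz = 0.30, power is 48%.

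**The case against.** The strongest reply is that the named family is not foreign to the plan. AUDIT predicting slope is AUDIT × time, a between-person variable interacting with a within-person one. The mismatch is grouped against continuous, not one unrelated test against another. This stands, and it is why AUDIT-by-slope is the closest planned test.

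Three further points also stand:

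- A reader might infer that the study plans no other between-person analysis. It does. Section 8.1 lists exploratory correlations, chi-square tests and ANOVA on participant characteristics, Section 4.3 mentions moderators in secondary analyses, and the Aim 5 regression does not exclude between-person variation. The point is therefore limited to aim-specific hypothesis tests. Section 8.2 does not link its figure to the exploratory analyses either.
- A reader might infer that 86% is a miscalculation. Step 1 does not support that. Three AUDIT zones by two sexes make six cells, and Section 4.3 has five paced drinks, so a 6 × 5 layout could have been used. That is a guess, and no such grouped test is planned.
- The low AUDIT power rests on the correlation and regression conventions for medium. Under the convention in step 3 it is 88.5%. The plan does not say which effect it means.

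The study also describes itself as gathering pilot data, which lowers the stakes. But Section 8.2 still presents 42 as the minimum needed to test the aims.

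**Conclusion.** The point holds in this limited form. The 86% belongs to a grouped test outside the aim-specific plan and to an effect size with no number. For the nearest planned test, power at N = 42 and two-sided alpha 0.05 is about 49% to 51% at r = 0.30 and 69% at f² = 0.15; 86% needs r of about 0.43 to 0.45. These figures assume 42 completers and one slope per person with no loss from measurement error.

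It would be tempting to conclude that N = 42 is too small for the study. The documents do not support that: a two-level within-person contrast has about 89% power at dz = 0.50. The shortfall concerns what the power statement covers and how its effect is defined.

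**What to change.** Keep N = 42 and replace the single 86% statement in Section 8.2 with power by planned test, each under a stated numeric effect size:

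- **AUDIT by slope (Aim 3), reported separately:** about 50% at r = 0.30, 69% at f² = 0.15, and 86% at r of about 0.43 to 0.45.
- **Two-level within-person contrasts:** about 89% at dz = 0.50. For Aim 4, first reconcile the factor label. Section 8.1 writes the levels as alcohol and placebo, while the stated prediction compares supplement with placebo.
- **Aims 1, 2 and 5:** state that the calculation does not cover them. Leave their planned tests as they are, since Section 8.1 says the Aim 1 and 2 models will test those associations.

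If the 86% is kept, give f, the number of groups and measurements, ρ and ε, and name the analysis that it applies to.

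The cost is protocol wording only, with no added participants or procedures. The downside is that one stated power figure becomes less favourable.

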8.3 PLANS FOR DATA MANAGEMENT

Questionnaire data will be digitally captured via REDCap a secure, HIPAA compliant web-interface that connects to UNC. In case of a device malfunction, a paper copy will be used, followed by manual data entry into REDCap by a member of the study team. Protected health information (PHI) from the online prescreen survey will be stored in REDCap. Participants will be assigned a numeric code which will be used to identify the study participants. This follows best practices and will minimize the risk of accidental disclosure of study participation or study measurements.

BACtrack Skyn Data: Skyn data are uploaded into a cloud-based server that is password and user account protected. The user account will be created by the PI and data will only be accessible by using this account login information. Only investigators with the IRB clearance will be given access to the password-protected secured server, which will be administered by the PI. BACtrack Skyn personnel do not access or export data collected for research studies.

EMA/Daily Diary Data: EMA and daily diary data collected via the LifeData application are stored in the Microsoft Azure cloud environment on services located in the United States. LifeData uses encryption technology for all data, including those on mobile databases, web databases, and in transit. All data are stored in the cloud environment and are back-up. The LifeData platform is password and user account protected and the web application employs an idle timeout. The user account will be created by the PI and data will only be accessible using this account login information. We will use the Anonymous Data Collection mode, which allows participants to download and interact with the LifeData mobile application without having to provide PII by creating a unique LifeData ID code that is distinct from their participant ID code. The LifeData ID code will be stored in the participant's REDCap file to facilitate linking data upon study completion. Data for each participant will be stored with their unique study identifier to maintain confidentiality. The LifeData platform is HIPAA compliant, GDPR compliant, and certified with a Privacy Shield.

9 SUPPORTING DOCUMENTATION AND OPERATIONAL CONSIDERATIONS

9.1 REGULATORY, ETHICAL, AND STUDY OVERSIGHT CONSIDERATIONS

9.1.1 INFORMED CONSENT PROCESS

9.1.1.1 CONSENT/ASSENT AND OTHER INFORMATIONAL DOCUMENTS PROVIDED TO PARTICIPANTS

Informed consent is a process that is initiated prior to the individual's agreeing to participate in the study and continues throughout the individual's study participation. The informed consent procedures will be conducted in-person or remotely using a HIPAA-compliant virtual meeting platform (e.g., Webex, Zoom) and REDCap. Consent forms describing, in detail, the study procedures, and risks are given to the participant and written documentation of informed consent is required prior to the administration of any treatment. All consent forms will be IRB-approved and updated with any new information as modifications are made throughout the study.

9.1.1.2 CONSENT PROCEDURES AND DOCUMENTATION

Participants must complete the consent documentation prior to any in-person study session procedures taking place. Participants will provide electronic signature (via REDCap) witnessed by research personnel. At several intervals during the consent review, the researcher will ask questions that will assess the comprehension of the information in the consent. If the participant is unsure or does not know, the researcher will return to that section and more carefully explain the information. The researcher will also pause several times during the consent process and ask if the participant has any questions about the study or their participation. If needed, the participants will have the opportunity to discuss the study with their surrogates or think about it prior to agreeing to participate. Participants will be informed that participation is voluntary and that they may withdraw from the study at any time, without prejudice or penalty. A copy of the signed informed consent document will then be given to the participant for their records.

9.1.2 STUDY DISCONTINUATION AND CLOSURE

This study may be temporarily suspended or prematurely terminated if there is sufficient reasonable cause. If the study is prematurely terminated or suspended, the Principal Investigator (PI) will promptly inform research staff, study participants, and the IRB and will provide the reason(s) for the termination or suspension. Study participants will be contacted, as applicable, and be informed of changes to study visit schedule.

Circumstances that may warrant termination or suspension include, but are not limited to:

- Determination of unexpected, significant, or unacceptable risk to participants
- Insufficient compliance to protocol requirements
- Data that are not sufficiently complete and/or evaluable

Study may resume once concerns about safety, protocol compliance, and data quality are addressed, and satisfy the IRB.

9.1.3 CONFIDENTIALITY AND PRIVACY

The database will be password protected. Additionally, REDCap's unique features will be used to ensure that PHI cannot be exported from the database. Written records will be kept in locked files that are only accessed by study staff. All staff associated with this study have been trained in ethics and protection of personal health information. All identifiable data will be locked in cabinets (for hard copy) or on a password-protected secure server (for electronic data). All data storage methods noted above are password protected and will be accessed using secure devices that meet the IRB determined data safety level. Data will only be transmitted between members of the research team in de-identified form.

9.1.4 FUTURE USE OF STORED DATA

After the study is completed, the data collected for this study will be fully de-identified and archived within a locked file cabinet or an encrypted server maintained by the principal investigator. Physical files with linking or identifying information will be shredded and digital files with linking or identifying information will be permanently deleted.

9.1.6 SAFETY OVERSIGHT

Safety oversight will be under the direction of the principal investigator and co-investigator. The PI and/or Co-I will review unanticipated problems in real time and make decisions as of participant's continuation of the study session. The PI will review AEs with the research team as soon as possible after identification. Any protocol deviations will be reviewed at regular intervals. The PI may request additional review by Co-I on a case-by-case basis. Additional information about reporting procedures are outlined in section 9.1.9.1.

9.1.7 CLINICAL MONITORING

Clinical site monitoring is conducted to ensure that the rights and well-being of trial participants are protected, that the reported trial data are accurate, complete, and verifiable, and that the conduct of the trial is in compliance with the currently approved protocol/amendment(s), with International Conference on Harmonisation Good Clinical Practice (ICH GCP), and with applicable regulatory requirement(s). This is a single site, investigator initiated, experimental research study so there will be no site monitoring plan in place.

9.1.7.1 STUDY MONITORING PLAN

The latest version of the approved IRB application for this study will be followed at all times. This responsibility falls in the hands of the trained research personnel. If at any time there is a deviation from protocol, the deviation from protocol log will be filled out. All team members will be trained on how and when to use this log. Deviations will be sent to IRB every 4-6 weeks (if necessary).

Data will be verified for completeness following every study session and all data will be entered into REDCap, a secure online database. After a participant has completed their participation (full completion through the in-person study visit or because they withdrew prior to completion), data will be rereviewed for completeness and accuracy. After all data has been collected, data will be re-reviewed by another lab member who was not involved with the data collection process.

The PI and Co-I will have read-only access to the REDCap database. This allows the PI and Co-I to view reports that provide information on any missing data on an individual participant basis, but does not allow them to add, change or input any data.

9.1.8 QUALITY ASSURANCE AND QUALITY CONTROL

The Study team will conduct internal quality management of study conduct, data collection, documentation and completion. Following written Standard Operating Procedures (SOPs), research personnel will verify that the clinical trial is conducted and data are generated, documented (recorded), and reported in compliance with the protocol, International Conference on Harmonisation Good Clinical Practice (ICH GCP), and applicable regulatory requirements (e.g., Good Laboratory Practices (GLP), Good Manufacturing Practices (GMP)).

9.1.9 DATA HANDLING AND RECORD KEEPING

9.1.9.1 DATA COLLECTION AND MANAGEMENT RESPONSIBILITIES

Trained research personnel will be responsible for the informed consent process, review for eligibility, questionnaire administration, data entry, device administration, and CRF entries. Research personnel will be responsible for unanticipated problem documentation and reporting, while the PI will be responsible for the unanticipated problem assessment, review of the unanticipated problem documentation forms and overview of the research staff.

Clinical data (including unanticipated problems and concomitant medications) will be entered into a data capture system provided by TraCS Clinical Research Data Management Service (REDCap). The data system includes password protection and internal quality checks, such as automatic range checks, to identify data that appear inconsistent, incomplete, or inaccurate. Clinical data will be entered directly from the source documents. Trained research personnel will have complete access to the REDCap system, while the PI and Co-I will have read-only ability. This will enable the researchers to enter the data and the PI and Co-I to review.

As discussed in **Section 9.1.3**, data entered in REDCap is stored on servers that are maintained by TraCS. The data is encrypted during transmission. The servers are in a secure campus area with all appropriate physical security measures in place. The web and database servers are monitored by the TraCS IT staff, patched frequently, and scanned by a third-party vendor to ensure that they are protected against known vulnerabilities. The scanning application is the standard service for the entire campus.

9.1.9.2 STUDY RECORDS RETENTION

According to the University of North Carolina at Chapel Hill's Archives and Record Management Services schedule for General Records Retention and Disposition Schedule, records will be kept for 5 years after the completion of the study or grant end date, whichever is later.

9.1.10 PROTOCOL DEVIATIONS

All deviations from the protocol will be addressed in study participant source documents. The researcher will complete a Protocol Deviation Log using the participant code as the identifier. This form will collect information such as the date the deviation occurred, details of what the deviation consisted of, any corrective and preventative actions that were taken as a result of the deviation, and the date that the PI and IRB were notified. The PI will review the information and initial once approved. A completed copy of the Protocol Deviation Form will be maintained in the regulatory file, as well as in the participant's source document. Protocol deviations will be sent to the IRB per their guidelines. The site PI/study staff will be responsible for knowing and adhering to their IRB requirements.

9.1.11 PUBLICATION AND DATA SHARING POLICY

This study will comply with the NIH Data Sharing Policy.

